### **Schedule of data collection**

- At scheduling
  1. Spec & CL Rx within one year.
- Baseline Visit
  1. Screening for eligibility
    - Cover test: no strabismus
    - Steropsis: at least 40" of arc with no suppression
    - Refraction if last eye exam was > one year
  2. Enrollment & random assignment to a lens
  3. Informed consent
  4. CVS-Q
  5. Baseline tests through updated refraction
    - LogMAR Hi/Lo contrast at 40cm and & 6M
    - Range of clear vision
    - Defocus testing
    - Test accommodation
  6. Lens fitting of lens one. Trial lens ordering for both lens 1 and 2 if no power available in Rx.
- Second Visit: Scheduled 1-2 weeks after lens dispense, subject required to wear lens for minimum of 5 days, 10 hours per day. Minimum of 3 day washout from habitual CL.
  1. CVS-Q
  2. Tests through lens 1.
    - LogMAR Hi/Lo contrast at 40cm and & 6M
    - Range of clear vision
    - Defocus testing
    - Test accommodation
  3. Refit into lens 2.
- Second Visit: Scheduled 1-2 weeks after lens dispense, subject required to wear lens for minimum of 5 days, 10 hours per day. Minimum of 3 day washout from Lens 1.

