### Experimental design:

This is a randomized, double-masked, crossover clinical trial. Subjects (N= 30) will be randomly assigned to wear either the MyDay (stenfilcon A, Scottsville, NY) and then the MyDay Energys (stenfilcon A, Scottsville, NY) single vision contact lenses for a period of 5 days. Subjects will then be crossed over to the opposing design after a three-day wash-out period.

Symptoms and visual performance will be assessed at baseline and exit from each design using primary outcomes measures.

- **Computer vision syndrome questionnaire (CVS-Q)** is a reliable and valid tool for measuring frequency and intensity of visual symptoms related to computer use in the workplace.
- **Binocular logMar (H/Lo contrast) visual acuity at 6M and 40cm.** The M&S Technologies Smart System II (M&S Technologies, Niles, IL) has been shown to be comparable to ETDRS and Pelli Robson charts. Computer tests have been shown to a reliable, capable way of assessing vision.
- **Binocular range of clear vision.** Use a near card with subject observing an isolated 20/30 target on the phoropter near testing rod. Pull back until subject report blur (repeat 3 times). Push in until subject report blur (repeat 3 times).
- **Subjective assessment of accommodation** is assessed by plotting a binocular defocus curve over-refraction at 6M (-3.00 to +3.00D in 0.50D steps) in phoropter while wearing contact lenses. Room luminance will be controlled and subjects will view optotypes through a standardized 4 mm aperture to reduce confounding effects on retinal defocus. Lenses will be presented in a randomized order.
- **Objective assessment of accommodation** Multiple studies support quantitative and qualitative changes in accommodation may be associated with asthenopia. The Grand Seiko WR 5500 (AIT, Bensenville, IL) has been shown to be capable of reliably measuring objective accommodation.

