## Computer Vision Syndrome Questionnaire (CVS-Q)

*To be completed by subject*

Indicate whether you experience any of the following symptoms during the time you use the computer at work. For each symptom, mark with an **X**:

- a. First, the frequency, that is, how often the symptom occurs, considering that:
- NEVER = the symptom does not occur at all
  - OCCASIONALLY = sporadic episodes or once a week
  - OFTEN OR ALWAYS = 2 or 3 times a week or almost every day

- b. Second, the intensity of the symptom:

Remember: if you indicated NEVER for frequency, you should not mark anything for intensity.

	a. Frequency			b. Intensity	
	NEVER	OCCASIONALLY	OFTEN OR ALWAYS	MODERATE	INTENSE
1 Burning					
2 Itching					
3 Feeling of a foreign body					
4 Tearing					
5 Excessive blinking					
6 Eye redness					
7 Eye pain					
8 Heavy eyelids					
9 Dryness					
10 Blurred vision					
11 Double vision					
12 Difficulty focusing for near vision					
13 Increased sensitivity to light					
14 Coloured halos around objects					
15 Feeling that sight is worsening					
16 Headache					

Apply the following expression:  $\text{Score} = \sum_{i=1}^{16} (\text{frequency of symptom occurrence})_i \times (\text{intensity of symptom})_i$

*To be completed by investigator*

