#### Calculation of **TOTAL SCORE**

Considering that:

Frequency:

- Never=0
- Occasionally=1
- Often or always=2

Intensity:

- Moderate=1
- Intense=2

	Frequency	Intensity	Frequency x Intensity
1 Burning			
2 Itching			
3 Feeling of a foreign body			
4 Tearing			
5 Excessive blinking			
6 Eye redness			
7 Eye pain			
8 Heavy eyelids			
9 Dryness			
10 Blurred vision			
11 Double vision			
12 Difficulty focusing for near vision			
13 Increased sensitivity to light			
14 Coloured halos around objects			
15 Feeling that eyesight is worsening			
16 Headache			
$\text{Score} = \sum_{i=1}^{16} (\text{frequency of symptom occurrence})_i \times (\text{intensity of symptom})_i$			*

If the total score is  $\geq 6$  points, the worker is considered to suffer Computer Vision Syndrome

\* The result of Frequency X Intensity should be recoded as: 0 = 0; 1 or 2 = 1; 4 = 2

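### Study-lens wear may be as short as 5 days while the CVS-Q scores frequency by the week, and nothing ties exit answers to study-lens days

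*Combined protocol and SAP*

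**What the plan says.** Experimental design (protocol section) describes a randomized, double-masked crossover of two lenses, each worn as "single vision contact lenses for a period of 5 days", with a three-day washout between them. On outcomes it states: "Symptoms and visual performance will be assessed at baseline and exit from each design using primary outcomes measures". The CVS-Q is the first measure listed.

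Schedule of data collection turns the 5 days into a minimum and places each exit visit 1-2 weeks after dispensing. For the first lens it adds "Minimum of 3 day washout from habitual CL"; for the second, "subject required to wear lens for minimum of 5 days, 10 hours per day. Minimum of 3 day washout from Lens 1". At each visit the CVS-Q appears as a bare item with no further instruction. The recruitment script also gives 5 days per lens. The grant text (Statement of Research Plan, Experimental design) gives 1 month instead.

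The CVS-Q form opens with "Indicate whether you experience any of the following symptoms during the time you use the computer at work". Its two non-zero frequency grades are "OCCASIONALLY = sporadic episodes or once a week" and "OFTEN OR ALWAYS = 2 or 3 times a week or almost every day". The form names no recall window and no lens.

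**The concern.** An exit score is meant to describe symptoms in one lens. The form asks about computer use at work in general and grades frequency by the week, while the subject may have worn the lens for only five days after at least three days out of the previous one.

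Such a subject can reasonably answer in two ways: for the lens days alone, or for the last week or the usual state, which includes days out of the lens. The plan does not choose, so subjects may differ from one another and from their own baseline answer, which has no such limit. Days common to both exit scores, or unrelated to either lens, pull the two scores together and make a real symptom benefit harder to see. The dates of wear will not show which days a subject had in mind, so the analysis cannot repair this later.

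**Working it through.** **The plan's own figures.** The plan gives no effect size or SD for the CVS-Q. Its sample size rests on logMAR acuity (difference 0.1, SD 0.06) and states fewer than 27 subjects, raised to 30 for 10% dropout. The dropout step reproduces: 27 / 0.9 = 30. The figure of 27 serves below only as the number of completers.

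**Timing.** Inputs from the schedule: washout at least 3 days, wear at least 5 days, visit 7 to 14 days after dispensing. The text leaves open whether the washout comes before or after dispensing.
- Lens dispensed at the refit visit, washout first: the earliest compliant visit is day 3 + 5 = 8 and the latest is day 14. Wear is then 5 to 11 days.
- Lens dispensed after the washout: a subject wearing it daily has 7 to 14 days of wear. Less than a week arises only if days are skipped or wear stops at the floor.

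**Dilution at the floor.** Assume a 7-day recall, the five wear days being the last five before the visit, and a lens effect on the score proportional to the share of recalled days in the lens.
- Share in the lens: 5/7 = 0.71.
- Days out of the lens: 2/7 = 29%.
- With 7 or more days of wear up to the visit, or if only lens days are rated: share 1.00, no dilution.

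**Power, for illustration.** Paired t-test, two-sided 0.05, 27 completers. Power of 80% corresponds to a standardized paired difference of dz = 0.560. This dz is solved backwards from the power and is not taken from the plan.

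If every subject is at the floor and recalls a week, the mean difference is multiplied by 5/7. Let s be the share of the variance of the paired difference that is lens-specific and so shrinks by (5/7)² = 0.510. Then dz = 0.560 × 0.714 / √(1 − s + 0.510 s).

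| s | SD factor | dz | Power |
|---|---|---|---|
| 0 (SD unchanged) | 1.00 | 0.400 | 52% |
| 0.5 | 0.869 | 0.460 | 63% |
| 1 | 0.714 | 0.560 | 80% |

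With the SD unchanged, the sample needed for 80% power rises by (7/5)² = 1.96, to about 51 completers.

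**Counting lens days only.** Suppose a subject literally counts episodes, each day independent with probability r/7 for r episodes a week. The form's rule is "The result of Frequency X Intensity should be recoded as: 0 = 0; 1 or 2 = 1; 4 = 2". The expected item score is then P(≥1) for a moderate symptom and P(≥1) + P(≥2) for an intense one.

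| r per week | Moderate: 5 d / 7 d (ratio) | Intense: 5 d / 7 d (ratio) |
|---|---|---|
| 1 | 0.537 / 0.660 (0.81) | 0.689 / 0.924 (0.75) |
| 2 | 0.814 / 0.905 (0.90) | 1.256 / 1.545 (0.81) |
| 3 | 0.939 / 0.980 (0.96) | 1.650 / 1.856 (0.89) |
| 7 | 1.00 / 1.00 (1.00) | 2.00 / 2.00 (1.00) |

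Under this model both lenses' exit scores fall by 4% to 25% for symptoms occurring 1 to 3 times a week, and not at all for daily ones. The fall is the same for both lenses at equal wear.

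**The case against.** The strongest reply is that 5 days is a floor. With visits at 1-2 weeks, many subjects may wear the lens for a week or more, and for them the dilution vanishes under a weekly recall. This stands, and it limits the size of the point. It does not remove it: the design section and the recruitment script give 5 days as the period itself, nothing requires more, and longer wear does not supply the missing recall instruction.

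The form also asks for a usual rate, not a count over a window. A subject can judge roughly twice a week after five days, and five workdays make a full working week for a question about work. This also stands. A reader might infer from the second table that exit scores will fall by up to 25% and look like relief. The documents do not support that: it needs literal counting of infrequent symptoms, and the Statistical Analysis section specifies no change from baseline and no use of the CVS cut-off at exit.

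The CVS-Q is described as valid as printed, and an added line alters it slightly. That is a real but small cost.

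The grant text's 1 month would remove the mismatch, but three visits spaced 1-2 weeks apart cannot hold a month per lens, and the protocol section, schedule and script agree on 5 days.

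**Conclusion.** The point holds as a cheap improvement. The missing link between the exit CVS-Q and the study lens is the stronger part; the short minimum wear makes it matter.

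For subjects near the 5-day floor who recall a week, the between-lens difference can fall to 5/7 of its value. A reader might conclude that the trial's power on the CVS-Q drops to 52%. That is the worst case for a weekly recall: it puts every subject at the floor and holds the SD fixed, on an effect size the plan does not give. Under the same recall, power ranges from 52% up to no loss at all, depending on actual wear, how subjects answer, and how much of the variation is lens-specific.

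Nor do the documents support a claim of bias between lenses. Lens order is randomized and the same conditions apply to both periods. An apparent fall from baseline matters only if change from baseline is reported.

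**What to change.** 1. At both exit visits add one line to the CVS-Q: *answer for the past 7 days, while wearing the study lens*. At baseline use the same 7-day recall for the habitual correction.
2. Raise the minimum wear from 5 to 7 consecutive days, ending at the exit visit.
3. State whether the lens is dispensed before or after the washout. If it is dispensed at the refit visit with a 3-day washout, book the exit visit on days 10-14 (3 + 7 = 10), or days 11-14 if seven full wear days must precede it, instead of the days 8-14 feasible now.
4. Align the grant text's 1 month with the protocol.

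Costs: no extra visit, and the 1-2 week spacing stays. The booking window narrows from seven calendar days to five, or four under the stricter count. Up to 2 more days of lenses per period are needed: 30 × 2 × 2 = 120 pairs at most if replaced daily, and the manufacturer supplies the lenses. The schedule and recruitment script need an IRB amendment, and the recall line departs slightly from the questionnaire as printed. If longer wear is not acceptable, a line limiting answers to study-lens days would still remove most of the ambiguity.

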  1. CVS-Q
  2. Tests through Lens 2.
    - LogMAR Hi/Lo contrast at 40cm and & 6M
    - Range of clear vision
    - Defocus testing
    - Test accommodation

## Computer Vision Syndrome Questionnaire (CVS-Q)

*To be completed by subject*

Indicate whether you experience any of the following symptoms during the time you use the computer at work. For each symptom, mark with an **X**:

- a. First, the frequency, that is, how often the symptom occurs, considering that:
- NEVER = the symptom does not occur at all
  - OCCASIONALLY = sporadic episodes or once a week
  - OFTEN OR ALWAYS = 2 or 3 times a week or almost every day

- b. Second, the intensity of the symptom:

Remember: if you indicated NEVER for frequency, you should not mark anything for intensity.

	a. Frequency			b. Intensity	
	NEVER	OCCASIONALLY	OFTEN OR ALWAYS	MODERATE	INTENSE
1 Burning					
2 Itching					
3 Feeling of a foreign body					
4 Tearing					
5 Excessive blinking					
6 Eye redness					
7 Eye pain					
8 Heavy eyelids					
9 Dryness					
10 Blurred vision					
11 Double vision					
12 Difficulty focusing for near vision					
13 Increased sensitivity to light					
14 Coloured halos around objects					
15 Feeling that sight is worsening					
16 Headache					

Apply the following expression:  $\text{Score} = \sum_{i=1}^{16} (\text{frequency of symptom occurrence})_i \times (\text{intensity of symptom})_i$

*To be completed by investigator*

#### Calculation of **TOTAL SCORE**

Considering that:

Frequency:

- Never=0
- Occasionally=1
- Often or always=2

Intensity:

- Moderate=1
- Intense=2

	Frequency	Intensity	Frequency x Intensity
1 Burning			
2 Itching			
3 Feeling of a foreign body			
4 Tearing			
5 Excessive blinking			
6 Eye redness			
7 Eye pain			
8 Heavy eyelids			
9 Dryness			
10 Blurred vision			
11 Double vision			
12 Difficulty focusing for near vision			
13 Increased sensitivity to light			
14 Coloured halos around objects			
15 Feeling that eyesight is worsening			
16 Headache			
$\text{Score} = \sum_{i=1}^{16} (\text{frequency of symptom occurrence})_i \times (\text{intensity of symptom})_i$			*

If the total score is  $\geq 6$  points, the worker is considered to suffer Computer Vision Syndrome

\* The result of Frequency X Intensity should be recoded as: 0 = 0; 1 or 2 = 1; 4 = 2

## C. Statement of Research Plan

### a. Statement of Problem:

Computer Vision Syndrome (CVS), also referred to as digital eye strain, is a group of vision-related issues arising from prolonged digital screen use. According to the American Optometric Association, many individuals experience discomfort that increases with extended screen exposure. With widespread use of digital devices across all age groups, individuals spend over five hours per day on screens, exacerbating CVS symptoms.

Contact lens manufacturers continue to develop designs aimed at mitigating CVS symptoms by reducing higher-order aberrations, accommodative/convergence demands, and improving tear film stability. However, comparative studies evaluating these claims are limited due to variability in lens properties. This study aims to assess the validity of these claims by comparing symptoms and visual performance of two novel stenfilcon A lens designs.

### b. Experimental design:

This is a randomized, double-masked, crossover clinical trial. Subjects (N= 30) will be randomly assigned to wear either the MyDay (stenfilcon A, Scottsville, NY) and then the MyDay Energys (stenfilcon A, Scottsville, NY) single vision contact lenses for a period of 1 month. Subjects will then be crossed over to the opposing design after a three-day wash-out period.

Symptoms and visual performance will be assessed at baseline and exit from each design using primary outcomes measures.

- **Computer vision syndrome questionnaire (CVS-Q)** is a reliable and valid tool for measuring frequency and intensity of visual symptoms related to computer use in the workplace.
- **Binocular logMar (H/Lo contrast) visual acuity at 6M and 40cm.** The M&S Technologies Smart System II (M&S Technologies, Niles, IL) has been shown to be comparable to ETDRS and Pelli Robson charts. Computer tests have been shown to a reliable, capable way of assessing vision.
- **Subjective assessment of accommodation** is assessed by plotting a binocular defocus curve over-refraction at 6M (-3.00 to +3.00D in 0.50D steps) in phoropter while wearing contact lenses. Room luminance will be controlled and subjects will view optotypes through a standardized 4 mm aperture to reduce confounding effects on retinal defocus. Lenses will be presented in a randomized order.
- **Objective assessment of accommodation** Multiple studies support quantitative and qualitative changes in accommodation may be associated with asthenopia. The Grand Seiko WR 5500 (AIT, Bensenville, IL) has been shown to be capable of reliably measuring objective accommodation.

*Inclusion criteria:*

- Score of >6 on CVS-Q
- Male or female
- Age >18 years to 35 years of age
- Experienced, well-adapted contact lens wearers
- Spherical equivalent refractive error between  $\pm 6.00$ DS with astigmatism < -0.75D
- Normal stereopsis and binocular status

*Exclusion criteria:*

- Monovision
- History of refractive surgery
- Binocular vision abnormalities
- Ocular or systemic disease
- Allergic reactions of ocular surfaces or adnexa that may be induced or exaggerated by wearing contact lenses or use of contact lens solutions.
- If eyes become red or irritated.
- The patient is unable to follow lens care regimen or unable to obtain assistance to do so

*Sample size:*

Sample size calculations were based on logMAR visual acuity values from Elliott et al. (1995). Assuming a clinically significant difference of 0.1 logMAR and a standard deviation of 0.06, a two-tailed t-test with  $\alpha=0.05$  and  $\beta=0.20$  indicates a sample size of <27 subjects. To account for a 10% dropout rate, 30 subjects will be enrolled.

*Statistical Analysis:*

Descriptive statistics will be provided for the cohort including age, gender, equivalent spherical refraction, hours spent using a smart device per day, and average wearing time per day. Primary outcome measures will be compared using either parametric or non-parametric testing after testing sample distributions for normalcy. Correlations between CVS-Q and outcome measures will be assessed.

This study will comply with the tenets of the Helsinki Declarations and will be approved by the Institutional Review Board.

**c. Institutional and other resources available:**

All patient visits will be conducted at the Southern College of Optometry (SCO). The M&S Technologies Smart System II needed for binocular visual acuity testing and subjective assessment of accommodation, in addition to the Grand Seiko WR 5500 needed for objective assessment of accommodation, will also be

provided by the Southern College of Optometry. The study contact lenses will be provided by CooperVision. Funding for student research participation and conference travel is supported by the SCO Summer Research Fellowship Program.

- d. **Relevance of Problem to Optometry or Vision Science:** Computers, tablets, e-readers, and cell phones garner an ever-increasing presence in patients' day-to-day lives. Optometrists and vision scientists are likely to be confronted with increasing levels of Computer Vision Syndrome in patient care. Research on the impact of contact lens designs on CVS symptoms is essential for guiding clinical recommendations. This study will contribute valuable data regarding the efficacy of novel lenses like Biofinity Energys and MyDay Energys in alleviating CVS.
- e. **Plans for Publication:** An abstract describing the primary outcome will be submitted to Academy 2026 Anaheim, and a manuscript on the same topic will be submitted to Contact Lens & Anterior Eye.

f. **Time Table:**

	2025	2025	2025	2025	2025	2026
	April	May	June	July	Aug	May
Activity						
IRB Preparation						
Data Collection						
Data Analysis						
Final Study Report						

D. **Budget**

Projected Expenses	Cost per unit	Units	Total	Source of funding
Research Subject Compensation	\$50 (3 visits)	30 subjects	1500	
Statistician (\$125/hour)	\$125/hour	2 hours	250	
Fluorescein Strips	\$80	1 box	80	
Contact lens cases	0.21/each	90	19	
		Total	\$1849	BSK grant

**Overhead Fees covered by SCO**

- Research Coordinator time
- Contact Lens Staff time
- Facility fees
- Student researcher time and fund
- Conference presentation and travel fees
- Manuscript publication fees

**E. Requested Support from Beta Sigma Kappa**

**Amount of Funding Requested:** \$1849

[figure not shown]
**Describe/Itemize the costs comprised in this amount:**

- Research subject compensation: Used to reimburse subjects for their time and effort to participate in the research project. The projected time needed is one hour per visit. Subjects (N = 30) would receive \$15 via Visa gift card for each of the first two completed visits, and \$20 on the last visit upon completion of the study. Subjects completing all three visits would receive a total of \$50.
- Statistician: To aid in robust analysis of the final research data. Hiring an independent statistician to perform data analysis will aid in manuscript acceptance and publication.
- Supplies for research study
  - Fluorescein strips: To be used to assess ocular health.
  - Contact lens cases: To be used for subjects to remove and store their contact lenses for the assessment of ocular health.

**Justification for equipment, supplies and other expenses:** Because this project includes multiple, long visits and extended commitment from research subjects, financial incentive will likely aid in greater recruitment and retention. The prospect of reimbursing subjects for their time is also likely to speed up enrollment, ensuring that the project can stay on track for completion in a timely manner.

**Plan for additional funding:** In the unlikely event that the expense for their project exceeds the amount of the budget, additional funding will be sought through additional grants or the Southern College of Optometry.

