**Describe any equipment to be used on the subjects, calibration procedures, & safety checks.**

- **Computer vision syndrome questionnaire (CVS-Q)** is a reliable and valid tool for measuring frequency and intensity of visual symptoms related to computer use in the workplace.
- **Binocular logMar (H/Lo contrast) visual acuity at 6M and 40cm.** The M&S Technologies Smart System II (M&S Technologies, Niles, IL) has been shown to be comparable to ETDRS and Pelli Robson charts. Computer tests have been shown to a reliable, capable way of assessing vision.
- **Binocular range of clear vision.** Use a near card with subject observing an isolated 20/30 target on the phoropter near testing rod. Pull back until subject report blur (repeat 3 times). Push in until subject report blur (repeat 3 times).
- **Subjective assessment of accommodation** is assessed by plotting a binocular defocus curve over-refraction at 6M (-3.00 to +3.00D in 0.50D steps) in phoropter while wearing contact lenses. Room luminance will be controlled and subjects will view optotypes through a standardized 4 mm aperture to reduce confounding effects on retinal defocus. Lenses will be presented in a randomized order.
- **Objective assessment of accommodation** Multiple studies support quantitative and qualitative changes in accommodation may be associated with asthenopia. The Grand Seiko WR 5500 (AIT, Bensenville, IL) has been shown to be capable of reliably measuring objective accommodation.

**Identify all personnel who will be collecting data from subjects or operating equipment and their special skills or qualifications. (Add extra pages if needed.)**

[name]

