## Application for Initial SCO IRB Review: Protocols Involving Human Subjects

Informed consent containing the basic elements and applicable additional elements as outlined in the SCO IRB document "Elements of Informed Consent" must be obtained from subjects BEFORE participation in any study. However, if ALL of the necessary criteria are met, you may apply for permission to alter some or all of the elements or to have the informed consent requirement waived altogether. Click the button to the left to see the criteria necessary to waive or alter the IC:

Criteria for waiver/alteration IC

If you wish to apply for a WAIVER or ALTERATION of the informed consent document and process, specify whether you are requesting a waiver or an alteration and give the rationale below:

Click or tap here to enter text.

If you plan to obtain informed consent, but wish to waive DOCUMENTATION of informed consent, give your rationale below:

Click or tap here to enter text.

List the TOTAL number of subjects AT SCO that you wish to enroll: 30

Is this a MULTI-CENTER study? ☐ Yes ☒ No

If yes, list the TOTAL enrollment at all sites: Click or tap here to enter text.

Will the GENDER or RACE of the subjects be limited? ☐ Yes ☒ No

If yes, give rationale: Click or tap here to enter text.

Check each of the populations below that will be used in your research:

- |   |  |   |
|---|--|---|
|  Adults with cognitive impairment |  Patients                                |  SCO or TEC employees |
|  Pregnant women or neonates       |  SCO students                 |  Other                |
|  Prisoners                        |  Minors (<18 yrs)                        |   |
|  Non English-speaking subjects    |  Anyone likely to need surrogate consent |   |

Check all of the following subject recruitment methods that will be used. You will also need to ATTACH a copy of all printed ads, text-based messages, scripts of announcements and voice/verbal recruitment messages, etc.

- |  |   |                                    |
|--|---|------------------------------------|
|  Flyers, banners, or other postings            |  Email |  Telephone |

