### *Exclusion criteria:*

- Monovision
- History of refractive surgery
- Binocular vision abnormalities
- Current ocular or systemic disease that may affect the eye
- Allergic reactions of ocular surfaces or adnexa that may be induced or exaggerated by wearing contact lenses or use of contact lens solutions.

- If eyes become red or irritated.
- The patient is unable to follow lens care regimen or unable to obtain assistance to do so

*Sample size:*

Sample size calculations were based on logMAR visual acuity values from Elliott et al. (1995). Assuming a clinically significant difference of 0.1 logMAR and a standard deviation of 0.06, a two-tailed t-test with  $\alpha=0.05$  and  $\beta=0.20$  indicates a sample size of <27 subjects. To account for a 10% dropout rate, 30 subjects will be enrolled.

*Statistical Analysis:*

Descriptive statistics will be provided for the cohort including age, gender, equivalent spherical refraction, hours spent using a smart device per day, and average wearing time per day. Primary outcome measures will be compared using either parametric or non-parametric testing after testing sample distributions for normalcy. Correlations between CVS-Q and outcome measures will be assessed.

This study will comply with the tenets of the Helsinki Declarations and will be approved by the Institutional Review Board.

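### The baseline schedule lists screening and random assignment before informed consent; secondarily, the visible schedule does not itemise the budgeted ocular-health check

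*Combined protocol and SAP*

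**What the plan says.** **Consent order.** The Schedule of data collection gives the baseline visit six numbered steps. Step 1 is eligibility screening (cover test, stereopsis, and a refraction in some cases). Step 2 is "Enrollment & random assignment to a lens". Step 3 is "Informed consent". The CVS-Q, the baseline tests and the fitting of the first lens follow as steps 4 to 6. The IRB application says that informed consent "must be obtained from subjects BEFORE participation in any study". Its two fields for requesting a waiver, one for consent and one for its documentation, hold only the form's placeholder text.

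**Ocular health.** The grant application, under itemised costs, lists fluorescein strips for assessing ocular health. It says of the lens cases: "To be used for subjects to remove and store their contact lenses for the assessment of ocular health". The schedule for the lens 1 visit lists the CVS-Q, the through-lens tests and the refit into the second lens. The lens 2 visit lists the CVS-Q and the through-lens tests. The protocol's Exclusion criteria include the line "If eyes become red or irritated", without saying who judges it, when, or where the decision is recorded.

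**The concern.** The schedule is the working procedure that staff follow at the visit, and its order contradicts the rule in the same IRB application. Two things are at stake.

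- **Subjects.** As numbered, a person undergoes study screening and is allocated to a lens before agreeing to take part.
- **The randomised set.** A person who declines at step 3 has already been assigned. That is a loss after randomisation, with no consent to use any data. The visible Sample size and Statistical Analysis text does not say whether such a person is counted or replaced.

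The ocular-health matter is smaller. The exclusion line on redness or irritation appears to apply after entry, because it speaks of eyes that become red. A natural time to apply it is before the second lens is fitted, but no listed step there does so. Supplies for an eye check are budgeted, yet the visible schedule does not say when the check takes place.

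**Working it through.** **1. Consent order, side by side.**

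| Baseline step | Content | Before consent? |
|---|---|---|
| 1 | Eligibility screening | Yes |
| 2 | Enrollment and random assignment | Yes |
| 3 | Informed consent | – |
| 4 | CVS-Q | No |
| 5 | Baseline tests | No |
| 6 | Fitting of lens 1 | No |

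The other steps run in a sensible time order (questionnaire, tests, fitting), so the list reads as a sequence. Two of six steps precede consent. One could debate whether a cover test and a stereopsis test already count as participation. Random assignment clearly does. Fitting comes at step 6, so a person who refuses at step 3 has not yet received a study lens.

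**2. What a refusal would cost in numbers.** Inputs from Sample size: 30 enrolled, 10% dropout, fewer than 27 required.

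- Allowance: 30 × 0.10 = 3, leaving 30 − 3 = 27.
- The documents give no refusal rate. With 0, 1, 2 or 3 refusals after assignment, 30, 29, 28 or 27 assigned subjects remain, before any ordinary dropout.
- Each refusal is 1/30 = 3.3% of those assigned and uses one of the three spare places.

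Power for acuity is not threatened on the plan's own inputs (difference 0.1 logMAR, SD 0.06, two-sided alpha 0.05, power 0.80). The plan does not say whether 0.06 is the SD of the paired differences.

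- If it is, the effect size is 0.1/0.06 = 1.67, and a paired t-test needs 5.05 subjects, rounded up to 6.
- If the SD of differences is 0.06 × √2 = 0.085, the effect size is 1.18, and the test needs 7.78, rounded up to 8.

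Both are well below 27. The visible sample-size text rests on acuity alone, so this says nothing about power for the CVS-Q or the other outcomes.

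**3. The budget for an eye check.** Inputs from the grant application's Budget.

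- Lens cases: 90 × $0.21 = $18.90, shown as $19.
- Total: 1500 + 250 + 80 + 19 = $1849, which reproduces the stated total.
- 30 subjects × 3 visits = 90, so the number of cases is consistent with one check per subject per visit. The grant application does not state how many checks are intended.
- Supplies for the check: $80 + $19 = $99.

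**4. Where the check is listed.** None of the three visits in the visible schedule itemises it. The grant application's own Experimental design text does not list it either, although the same application budgets for it. Absence from a list of procedures is therefore weak evidence that no check is intended.

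**The case against.** **On consent.** The order may be a numbering slip. The IRB form states the right rule, no waiver is sought, and the consent pages are not in the text available here. All of that stands as a reason to doubt that anyone would be randomised without consent in practice. It does not make the schedule correct: the numbered list is what staff would follow, and it is wrong as written.

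**On ocular health.** Here the other side is stronger, and several larger inferences fail.

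- *A reader might infer that no eye-health check is done.* The schedule is headed as one of data collection, its fitting steps are single lines that may include an unwritten check, and pages are missing that could describe one.
- *A reader might infer that the protocol dropped a planned check.* The grant application is a differing version (1 month of wear, against 5 days in the protocol). It shows that a check was foreseen and nothing more.
- *A reader might take the IRB item "Describe any equipment to be used on the subjects, calibration procedures, & safety checks" as a place where an eye examination should appear.* In that sentence, safety checks can be read as checks of the equipment. The recruitment email is not a procedure list either.
- *A reader might infer that a subject whose eyes reacted to lens 1 would be refitted.* If the exclusion line applies after entry, it already bars that. Visible redness can be noticed without dye, and the CVS-Q at each visit asks about redness, burning and pain. What is missing from the visible schedule is a listed step that applies the criterion.
- *A reader might infer from "Refraction if last eye exam was > one year" that a refraction replaces an overdue eye exam.* The line can equally serve the "Baseline tests through updated refraction". The scheduling step asks for a prescription within one year, and the recruitment script makes an exam within 12 months an entry item.

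**Conclusion.** The consent order holds firmly. The baseline schedule places screening and random assignment ahead of consent, against the IRB application's own rule and with no waiver rationale entered. The severity is minor. It is an error in a working procedure, correctable by reordering. The numerical cost is at most one spare place per refusal out of three, and the number of refusals is unknown. No bias in the lens comparison is claimed: the design is described as double-masked, and each subject is due to wear both lenses.

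The ocular-health part holds as documentation only. The visible schedule does not list the assessment for which supplies are budgeted, and it has no step that applies the redness or irritation line before the refit. The documents do not show a safety gap, and no harm rate can be drawn from them.

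The conclusion assumes that the baseline numbering is meant as a time order and that the unavailable pages do not replace this schedule.

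**What to change.** 1. In the Schedule of data collection, renumber the baseline visit: informed consent as step 1, eligibility screening as step 2, enrollment and random assignment as step 3. The later steps stay as they are. This costs an edit to the schedule and an IRB amendment. It adds no visit time and no money.
2. If the ocular-health assessment is planned, list it. At the lens 1 visit it belongs after the through-lens tests and before the refit, with one recorded entry saying whether the redness or irritation criterion is met. The investigator sets the action for a given finding. If it is also planned at the other visits, list it there too. Should the unavailable pages already describe it, a cross-reference is enough.

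The second item can go into the same amendment. Supplies of $99 are already in the requested grant budget. The documents do not give the time for the check, which would have to fit within the one-hour visit. If fluorescein is used before the refit, it must be rinsed out before the second lens is placed.
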